Specific Aim 1: Improve detection of metastasis with fluciclovine and PSMA PET versus best standard of care conventional imaging, as confirmed with histology. We will image 20 patients with ILC who have either: a) clinical or imaging suspicion of metastatic disease; or b) proven metastatic disease but in whom there is suspicion of an even greater tumor burden that could change therapy approach. Abnormal foci which correlate to anatomic lesions previously unsuspected on conventional imaging will undergo optional biopsy as clinically indicated in the safest manner possible (if not already done) to determine the verified detection rate of metastatic disease.

Specific Aim 2: Determine concordance and discordance of ILC detection with PSMA versus fluciclovine PET, as confirmed with histology. We will compare verified detection rates for metastasis between fluciclovine and PSMA PET modalities. This may necessitate a second biopsy of a

[figure not shown]
distant lesion discordant between the 2 PET techniques. We will also analyze images for biodistribution in the primary lesion(s) for both radiotracers.

Exploratory Aim 3: Establish the role of molecular detection by ctDNA mutations including PIK3CA, ESR1, HER2, and AKT1 in characterizing the degree of tumor burden as identified by metabolic amino acid transport and/or tumor neovasculature receptor imaging [12]. We will collect peripheral blood for ctDNA in all patients and determine if ctDNA correlates with presence or absence of metastases and tumor burden as identified by fluciclovine (metabolic) and/or PSMA (angiogenesis) PET.

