1.2 Schema

We will undertake a single arm feasibility study with n=20 patients with treatment naïve biopsy proven ILC who have either: a) clinical or imaging suspicion of metastatic disease; b) biopsy proven metastatic disease but in whom there is suspicion of an even greater tumor burden that could change therapy approach. All patients will be recruited from the Winship Glenn Family Breast Cancer Program at any Emory facility and they will have already undergone best standard of care conventional imaging (CT or MR and possibly bone scan depending on clinical presentation). **Standard of care conventional imaging typically does not include FDG PET, since FDG PET is not recommended for lobular cancer due to low sensitivity.** We will then complete both fluciclovine PET and Ga PSMA PET scans on the same patient on separate days separated by at least 10 half-lives to allow for radioactive decay. There is no need for randomization since each patient will undergo both imaging techniques, and the results will be interpreted blindly. Thus, radiopharmacy scheduling will dictate the order of the radiotracers to ensure the patient will undergo both imaging modalities in the shortest time frame. Sometimes this will mean PSMA is completed first, followed by fluciclovine, and other times the opposite. After interpretation of both studies, careful correlation to already obtained conventional imaging will then be done to determine if a previously unsuspected anatomic correlate can be identified which would impact therapy. One or two metastases (depending on scan findings) will then undergo biopsy in the safest manner possible as standard of care (if not already done) to determine the verified detection rate of metastatic disease. Uncommonly, definitive imaging such as MR for skeletal or liver lesions may be accepted in lieu of biopsy, if biopsy is not feasible. We will then compare verified detection rate of each PET study to conventional imaging and to each other. In addition, we will collect peripheral blood for ctDNA in all patients and determine if ctDNA correlates with presence or absence of metastases and tumor burden as identified by conventional imaging, fluciclovine and/or PSMA PET. Study Specific Experimental Procedures will only consist of both PET studies and ctDNA analysis. All other procedures will be conducted per standard of care. See Figure 1.

Figure 1: Trial Schema, Flow diagram

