2) Allergic or other reactions to radiotracer: Although the risk is extremely small, it is possible to develop an allergic reaction to the fluciclovine or Ga-PSMA. This can result in hives, rash, itching and difficulty breathing which may require emergency medical treatment. There have been no previous instances of allergic reaction. In prior studies with both radiotracers, the risk of adverse events which can be attributed to the radiotracer is extremely low, and of minimal medical impact such as burning at IV site or dysgeusia.

3) Risk related to IV for PET scan: A small amount of radioactive material will be injected by either a hand-held needle or a machine. Such injections are generally quite safe, but any injection involves some risks. The injection could harm a nerve, artery or vein, or cause infection. The radioactive material could also leak from veins, causing swelling and discomfort.

4) False positive on PET: It is possible that a lesion identified on the experimental PET procedures may be false positive, thus potentially leading to an inappropriate change in stage. Yet, no lesion will be acted upon which could change therapeutic intent unless confirmed via histology or advanced imaging such as MR for certain bone lesions. See below for risks associated with biopsy or MR.

Non-Study Specific Procedure Risks:

1) Biopsy associated risk: If a suspect lesion is identified on either or both PET scans, definitive histologic proof in the safest manner possible will be sought if clinically indicated. Risks of biopsy, though small in expert hands, include bleeding, infection and even rarely death. Note that before biopsy is considered, careful scrutiny of the already obtained CT or MR will be undertaken to determine if an unsuspected anatomic correlate can be identified. This will then prompt a discussion between the patient and primary clinician on the benefits versus risks to definitively determine if a metastasis is present which could affect therapy. Biopsy will be undertaken in the least invasive manner possible as a standard of care procedure, reimbursed by third party payers.

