
Preference for biopsy will be given to discordant lesions. Uncommonly, in some lesions not deemed safe to biopsy, characteristic appearance on correlative imaging will be accepted as truth (e.g., MRI for certain skeletal or liver lesions). In select cases, a second biopsy of a discordant distant lesion may be required. For example, if there are 2 potentially impactful lesions which are fluciclovine positive/PSMA negative and fluciclovine negative/PSMA positive, respectively. Note that before biopsy is considered, careful scrutiny of the already obtained CT or MR will be undertaken to determine if an unsuspected anatomic correlate can be identified. This will then prompt a discussion between the patient and the referring clinician co-investigator on the benefits versus risks to definitively determine if a metastasis is present which could affect therapy. Biopsy may be undertaken in the least invasive manner as standard of care as clinically indicated, reimbursed by third party payers. Uptake parameters will be correlated with all proven primary, locoregional, and distant lesions. Verified detection rates for metastasis will be calculated for each modality.

In addition, we will collect 20 ml peripheral blood for ctDNA analysis in all patients at visit 1 (or possibly 2) to be initially processed and stored by [name] lab for off-site specialty analysis. Plasma levels of ctDNA will be measured using a targeted 28 gene panel to detect point mutations including mutations in PIK3CA, ESR1, HER2, and AKT1, genes associated with hormone therapy resistance and ILC [38, 39]. We will examine ctDNA results for association with presence or absence of locoregional metastasis on imaging as confirmed with histology, presence or absence of distant metastasis on imaging as confirmed with histology, correlation of presence or absence and absolute ctDNA with PET uptake.

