8.1 Schedule of Procedures

See above schedule of activities in Section 1.3 for **study specific experimental procedures**.

Standard of Care Procedures

1) Conventional imaging is broadly defined as mammography, ultrasound, bone scan, FDG PET, CT and/or MR: Any or all of these imaging studies may have been performed as standard of care at enrollment. These are not under control of study design. Conventional imaging and reports within 6 months of enrollment (ideally 2 months) will be reviewed to correlate to PET imaging. No additional interpretation will take place. Imaging reports for these studies will be utilized for comparative analysis.

2) Biopsy: After the PET studies, patients with abnormal findings on the PET scans will have the most distant and accessible lesion identified so that the patient may undergo biopsy in the safest manner possible (if not already done) as clinically indicated. Preference for biopsy will be given to discordant lesions. In some lesions not deemed safe to biopsy, characteristic appearance on correlative imaging will be accepted as truth (e.g., MRI for certain skeletal or liver lesions). In select cases, a second biopsy of a discordant distant lesion may be required. Note that before biopsy is considered, careful scrutiny of the already obtained CT or MR will be undertaken to determine if an unsuspected anatomic correlate can be identified. This will then prompt a discussion between the patient and the referring clinician co-investigator on the benefits versus risks to definitively determine if a metastasis is present which could affect therapy. Biopsy will be undertaken in the least invasive manner as standard of care, reimbursed by third party payers.

3) Therapy: All subsequent therapy for breast cancer will be standard of care and beyond the scope of this investigation.

9. Measurement of Effect

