Image Analysis: Two nuclear medicine physician co-investigators, [name], will independently interpret the 20 cases, each reading half (the other reading the other half) of the fluciclovine and PSMA images (to avoid bias in always reading the same type of imaging). The readers will be blinded to all imaging including the other PET. All suspicious lesions with nonphysiologic activity above background for locoregional spread and distant disease will be identified and rated for suspicion of malignancy on a 6 point Likert scale (where 1 = definitely benign and 6 = definitely malignant). Both the primary lesion and all suspected metastases will be measured on an advanced workstation and metabolic uptake parameters (SUV, MTV, TLA) recorded. After both studies have been interpreted blindly, the third nuclear medicine physician co-investigator, [name], will blindly interpret deidentified PET studies on every patient (alternating for a total of 10 each fluciclovine and PSMA PET). Afterward, an unblinded reconciliation interpretation will take place with all 3 readers. To ensure balance, 10 of the studies will be reviewed for consensus first showing Ga-PSMA, then fluciclovine; 10 of the studies will be reviewed in the opposite manner. In this manner, a preliminary sense of kappa can be developed between the third and the other 2 readers, yet will guarantee the highest degree of patient care as there are currently no validated criteria for interpreting fluciclovine or PSMA PET for breast cancer. This approach will help us adapt existing prostate specific criteria to that of breast cancer. Concordant and discordant lesions between each PET study and conventional imaging will be reported and potential biopsy sites, if any, recommended.

Correlation of histology with images: Uptake parameters as above will be correlated with all proven primary, locoregional, and distant lesions.

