ctDNA analysis: Plasma levels of ctDNA will be measured using targeted assays to detect point mutations including mutations in PIK3CA, ESR1, HER2, and AKT1, genes associated with hormone therapy resistance and ILC [12, 38, 39, 43]. Because ILC are predominantly hormone receptor positive, hormone resistance is particularly relevant because it predicts for higher rate of distant metastasis. [name], will provide expertise in ctDNA analyses. Deidentified specimens will be shipped to the Circulating Tumor Cell Center at Massachusetts General Hospital for fee for service ctDNA processing.

Correlation of ctDNA results with results of imaging: We will examine ctDNA results for association with presence or absence of locoregional metastasis on imaging as confirmed with histology, presence or absence of distant metastasis on imaging as confirmed with histology, correlation of presence or absence and absolute ctDNA with PET uptake as determined by the following indices: SUVmax, SUVmean, SUVpeak, Total Lesson Activity for the index primary, locoregional and distant metastatic lesion if any, and correlation to summed indices as a reflection of total metabolic tumor burden. ctDNA will also be correlated with CI.

10. Statistical considerations

Specific Aims 1 and 2

Analysis plan: The objectives of Aims 1 and 2 are to compare verified detection rates between fluciclovine and PSMA PET versus conventional imaging, as confirmed with histology (Aim 1), and determine concordance and discordance of ILC detection with PSMA versus fluciclovine PET, as confirmed with histology (Aim 2). Paired detection rates will be assessed using McNemar's test.

Detection rates will be reported for each method, and 95% confidence intervals will be estimated using the Clopper-Pearson approach. Rates of concordant/discordant observations will be reported. The Likert rating-scale data also allows for determination of sensitivity, specificity, PPV, NPV and Receiver Operating Characteristic (ROC) Area Under the Curve (AUC) values to compare.

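### No rule gives a reference status to lesions seen only on conventional imaging or to PET-negative patients, so the Aim 1 difference and the accuracy measures are open to verification bias of unknown direction and size

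*Combined protocol and SAP*

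**What the plan says.** **Analysis.** Section 10 assesses paired verified detection rates by McNemar's test: each PET against conventional imaging (Aim 1) and PSMA against fluciclovine (Aim 2). It does not state the unit, numerator or denominator of the rate. It adds: "The Likert rating-scale data also allows for determination of sensitivity, specificity, PPV, NPV", and ROC AUC.

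**Who is verified after PET.** Section 8.1: "patients with abnormal findings on the PET scans will have the most distant and accessible lesion identified so that the patient may undergo biopsy". Section 2.3: "If a suspect lesion is identified on either or both PET scans, definitive histologic proof in the safest manner possible will be sought", subject to clinical indication. For Aim 1 (sections 1.1 and 3.1): "Abnormal foci which correlate to anatomic lesions previously unsuspected on conventional imaging will undergo optional biopsy". Section 1.2 sets the number: "One or two metastases (depending on scan findings) will then undergo biopsy in the safest manner possible as standard of care".

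**Other routes to a reference status.**
- Sections 4.1 and 8.1 prefer discordant lesions for biopsy.
- Biopsies done before PET count, and inclusion criterion 2b admits patients with metastasis already proven.
- MR may stand in for biopsy at some bone or liver sites.
- Section 1.3 lists optional biopsy during follow-up, which runs through the medical record for up to 5 years. Section 4.4 continues follow-up until the endpoints can be determined, with no window or criteria.

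**What is scored and reported.** Section 9: "All suspicious lesions with nonphysiologic activity above background for locoregional spread and distant disease will be identified and rated" on the six-point Likert scale. Also in section 9: "Concordant and discordant lesions between each PET study and conventional imaging will be reported and potential biopsy sites, if any, recommended".

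**The concern.** McNemar's test uses only the discordant cells, here metastases detected by PET alone and those detected by conventional imaging alone. If confirmation is more likely in one cell than in the other, the verified difference departs from the true one even when every reading is correct.

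Post-PET biopsy is tied to an abnormal PET and, for Aim 1, aimed at foci that conventional imaging had not raised. The conventional-only cell depends on the other routes, and none of these is a classification rule. The same holds for a PET-negative patient without proven metastasis.

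Section 10 gives estimation of effect size as the pilot's purpose and turns the difference and discordance into sample sizes for a larger study. The main harm is therefore a biased pair of planning values. The accuracy measures have a related problem: sites without PET uptake get no score and have no defined reference.

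**Working it through.** **1. Reproduce the plan's figures.** Section 10 gives 67, 83 and 99 patients for a 20% difference at 40%, 50% and 60% discordance, 118 to 175 for 15%, and 42 to 63 for 25% (80% power, Type I error 0.05, sidedness not stated). With difference d and discordance D, the PET-only share of discordant pairs is (D + d)/(2D). Exact conditional McNemar power, summed over the binomial number of discordant pairs, with one-sided 0.05, gives exactly 67, 83, 99, 118, 175, 42 and 63. Two-sided exact gives 84 in place of 67. I use the one-sided version because it matches the plan.

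**2. Section 10's base scenario.** d = 20% and D = 40% mean PET-only (40 + 20)/2 = 30% and conventional-only (40 − 20)/2 = 10%.

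**3. Apply verification.** Let u and v be the shares of PET-only and conventional-only detections that are verified. Over all scanned patients:
- observed difference = 0.30u − 0.10v
- observed discordance = 0.30u + 0.10v

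The documents give no value for u or v, so these are assumed.

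| u | v | Difference | Discordance | Patients implied |
|---|---|---|---|---|
| 100% | 100% | 20% | 40% | 67 |
| 80% | 40% | 24 − 4 = 20% | 24 + 4 = 28% | 47 |
| 80% | 80% | 24 − 8 = 16% | 24 + 8 = 32% | 83 |
| 50% | 80% | 15 − 8 = 7% | 15 + 8 = 23% | 312 |

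In the second row the difference is right by coincidence, but the discordance is wrong and the sample size falls. In the third row verification is equal but incomplete, and the difference still shrinks because unverified detections stay in the denominator.

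**4. No true difference.** Assume 20% PET-only and 20% conventional-only. The observed difference is 0.20(u − v):
- u = 90%, v = 60%: +6 points
- u = v = 90%: 0
- u = 60%, v = 90%: −6 points

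**5. Sampling error.** At n = 20 in the base scenario, the standard error of the difference is √((0.40 − 0.20²)/20) = 0.134, a Wald 95% half-width of about 26 points.

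**6. Accuracy measures.** Assume true sensitivity 0.70, specificity 0.80, prevalence 0.60, with 90% of PET-positives and 20% of PET-negatives verified.
- TP = 0.60 × 0.70 × 0.9 = 0.378; FN = 0.60 × 0.30 × 0.2 = 0.036; sensitivity reads 0.378/0.414 = 0.91.
- FP = 0.40 × 0.20 × 0.9 = 0.072; TN = 0.40 × 0.80 × 0.2 = 0.064; specificity reads 0.064/0.136 = 0.47.
- NPV stays at its true 0.64 if PET-negatives are verified at random. If diseased PET-negatives are verified at 50% and the others at 20%, FN = 0.60 × 0.30 × 0.5 = 0.090 and NPV reads 0.064/0.154 = 0.42.

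**The case against.** **The plan already reaches the other cell.** In section 4.1 the preference for discordant lesions comes shortly after PET-versus-conventional discordance is mentioned, so it can be read as covering both directions. The section 8.1 trigger is a patient with an abnormal PET, and such a patient could have a conventional-only lesion sampled. Inclusion criterion 3 asks for willingness to undergo biopsy without reference to PET. With pre-PET biopsies, metastases proven at entry and follow-up, zero verification of that cell is unlikely. This stands, and it limits the claim. But the preference is not a rule, its only worked example sets one tracer against the other, and an unbiopsied lesion still has no status.

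**A reader might infer that the design must favour PET.** The documents do not support that. PET-only biopsy is optional, and first "careful scrutiny of the already obtained CT or MR will be undertaken to determine if an unsuspected anatomic correlate can be identified". Conventional-only lesions may already have been proven before PET. Either cell could be the better verified.

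**Twenty patients with no power analysis.** Sampling error exceeds the shifts in the table, and section 10's sample sizes are conditional illustrations. True, but a confidence interval shows sampling error. It does not show this bias, which does not shrink with more patients.

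**Accuracy can still be estimated.** Flagged lesions can score as low as definitely benign, so specificity and NPV conditional on flagged and verified lesions are obtainable. Patient-level sensitivity is obtainable in the subset with metastasis proven at entry. Both points stand.

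**Conclusion.** The concern holds as a missing reference rule, not as a demonstrated bias in PET's favour. As written, the PET-versus-conventional difference and the discordance rate can be biased either way by an unknown amount. In section 10's own scenario, the assumed verification shares move the implied larger study from 67 patients to 47, 83 or 312. These figures rest on chosen shares, one target metastasis per patient and the one-sided exact test that matches the plan. They show sensitivity to an undefined rule, not a forecast.

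A reader might also re-size the larger study by changing the difference alone and reading along section 10's rows. That is not sound, because incomplete verification changes discordance as well. False significance at n = 20 is a lesser matter than biased planning values.

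Unconditional sensitivity and specificity cannot be estimated without verification bias. NPV escapes only if PET-negatives are verified independently of disease, which is unlikely when conventional imaging or clinical suspicion prompts it. It would go too far to say that no accuracy measure can be estimated. Aim 2 is less exposed, since section 4.1 foresees biopsy of tracer-discordant lesions in both directions. The point should be fixed before analysis.

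**What to change.** In section 10:

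1. **Unit.** Make the patient the unit for McNemar: at least one confirmed metastasis detected by the modality, over all scanned patients. Keep lesion-level results descriptive and allow for clustering within patients.
2. **Reference status.** Seek a status for every lesion positive on PET or conventional imaging, and for PET-negative patients, from histology (including pre-PET), accepted MR, or record follow-up within a fixed window. Section 4.4 expects most relevant follow-up within 1 year. Report verified and unverified counts for each PET/conventional cell, and give best-case and worst-case bounds on the patient-level difference beside the McNemar result. Invented example, n = 20: 4 PET-only and 1 conventional-only patients verified, 2 and 3 unverified. Observed (4 − 1)/20 = +15 points; bounds (4 − 1 − 3)/20 = 0 to (4 + 2 − 1)/20 = +25 points.
3. **Incremental yield.** For each tracer, report patients with at least one confirmed metastasis at a site not known before PET, over all scanned patients, with a Clopper-Pearson interval (for example 4/20 = 20%, 5.7% to 43.7%). State that this measure cannot credit conventional imaging.
4. **Accuracy.** Report PPV of verified PET foci. Label any sensitivity, specificity, NPV or AUC as conditional on flagged and verified lesions.

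**Cost.** Lesion extraction from existing imaging reports and adjudication from existing records, with no extra scan, biopsy or reader. Follow-up after therapy is a weaker reference than histology, and section 2.1 itself says response may be hard to evaluate in this disease. With one or two biopsies per patient, the bounds may be wide. A patient-level unit hides extra lesions in patients with metastasis proven at entry, which is why item 3 is needed beside it.

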Prostate specific membrane antigen (PSMA) is a Type 2 transmembrane glycoprotein of the M28 peptidase family and is overexpressed on the cell surface of prostate cancer [32]. The name prostate-specific is a misnomer, since other cancers including breast cancer have upregulated PSMA receptors due to tumor angiogenesis. Most data regarding PSMA PET with breast cancer pertains to IDC. Wernicke studied 92 samples in 106 patients with breast cancer [7]. Immunohistochemistry (IHC) for tumor associated vascular endothelial cell PSMA receptors revealed staining in 74% of primary and 100% of brain metastasis. There was absence of PSMA staining in 98% of normal breast tissue. Wernicke noted there was no difference between PSMA staining for IDC and ILC, yet only 10 ILC samples were included. In another study of 72 patients with breast cancer, moderate to strong tumor associated neovasculature PSMA staining was present in 67% of distant metastasis versus 36% in primary tumor cells [9]. Yet, only 12 ILC patients were included and it was not clear if these patients had metastases. In a study of 315

cases by Tolkach of which 64 tumors were ILC, 64.6% of patients with IDC had PSMA staining, versus 42.2% of those with ILC [11]. Finally, in one of the few imaging studies, Sathekge reported in 81 lesions in 19 breast carcinoma patients that PSMA PET visualized 84% of lesions; yet again, only 2 ILC patients were included in this cohort. In a major review in the Journal of Nuclear Medicine, Salas-Fragomeni argues “this potential application of PSMA-targeted imaging in breast cancer should perhaps be most urgently explored, as the need for reliable agents for systemic staging in lobular breast cancer has been long-standing” [8]. Our study will address this urgent question, that of the utility of PSMA PET explicitly for ILC metastatic disease, as well as that of fluciclovine PET for ILC.

ctDNA

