4.1 Overall Design

We will undertake a study with 20 patients with treatment naïve biopsy proven ILC who have either: a) clinical or imaging suspicion of metastatic disease; b) biopsy proven metastatic disease but in whom there is suspicion of an even greater tumor burden that could change therapy approach. All patients will be recruited from the Winship Glenn Family Breast Cancer Program at any Emory facility. All patients will undergo Ga PSMA PET followed at minimum of 10 hours (to allow for radiotracer decay) by fluciclovine PET. (This may also happen in the opposite order, in which case 20 hours after fluciclovine will be needed to allow for decay.) There is no need for randomization since each patient will undergo both imaging techniques, and the results will be interpreted blindly. Thus, radiopharmacy scheduling will dictate the order of the radiotracers to ensure the patient will undergo both imaging modalities in the shortest time frame. Two nuclear medicine physician co-investigators, [name], will independently interpret the 20 cases, each reading half (the other reading the other half) of the fluciclovine and PSMA images (to avoid bias in always reading the same type of imaging). The readers will be blinded to all imaging including the other PET. All suspicious lesions with nonphysiologic activity above background for locoregional spread and distant disease will be identified and rated for suspicion of malignancy on a 6 point Likert scale (where 1 = definitely benign and 6 = definitely malignant). Both the primary lesion and all suspected metastases will be measured on an advanced workstation and metabolic uptake parameters (SUV, MTV, TLA) recorded. After both studies have been interpreted blindly, the third nuclear medicine physician co-investigator, [name], will blindly interpret **deidentified** PET studies on every patient (alternating for a total of 10 each fluciclovine and Ga-PSMA PET). Afterward, an unblinded reconciliation interpretation will take place with all 3 readers. To ensure balance, 10 of the studies will be reviewed for consensus first showing Ga-PSMA, then fluciclovine; 10 of the studies will be reviewed in the opposite manner. In this manner, a preliminary sense of kappa can be developed between the third and the other 2 readers, yet will guarantee the highest degree of patient care as there are currently no validated criteria for interpreting fluciclovine or PSMA PET for breast cancer. This approach will help us adapt existing prostate specific criteria to that of breast cancer. Concordant and discordant lesions between each PET study and conventional imaging will be reported and potential biopsy sites, if any, recommended. The most distant and accessible lesion may undergo biopsy in the safest manner possible (if not already done) as clinically indicated after discussion between the primary oncologist and patient.

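### Uptake is recorded only for the primary and for suspected metastases during the blinded read, so a proven metastasis negative on one tracer appears to have no value on it for the analysis planned on all proven lesions.

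*Combined protocol and SAP*

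**What the plan says.** Section 4.1 and the image-analysis paragraph of section 9 give the same sequence.

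1. Each PET is read blind: "The readers will be blinded to all imaging including the other PET".
2. Suspicion is tied to uptake: "All suspicious lesions with nonphysiologic activity above background for locoregional spread and distant disease will be identified".
3. Measurement follows directly: "Both the primary lesion and all suspected metastases will be measured on an advanced workstation and metabolic uptake parameters (SUV, MTV, TLA) recorded".
4. A third blinded read and an unblinded three-reader reconciliation come afterwards. Neither includes a measurement step.

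The next paragraph of section 9 sets the analysis: "Uptake parameters as above will be correlated with all proven primary, locoregional, and distant lesions". Section 4.1 has an equivalent sentence.

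The plan expects lesions that only one tracer shows. Section 4.1 gives the example of two lesions that are, respectively, "fluciclovine positive/PSMA negative and fluciclovine negative/PSMA positive". On which lesions are proven, sections 4.1 and 8.1 say: "Preference for biopsy will be given to discordant lesions".

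No section says whether a region is placed on a proven metastasis that was not called on a given tracer, or how its missing value enters means, sums or correlations.

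**The concern.** The set measured (suspected lesions) and the set analysed (proven lesions) differ, and the difference depends on the quantity being analysed. A metastasis at or below background on one tracer is not called on that scan. If it is later proven, through the other tracer or through conventional imaging, it belongs in the analysis but has no value on the negative tracer. The biopsy preference makes such lesions more frequent among the proven ones.

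Three things are at stake:

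- Any per-lesion SUV summary in proven metastases is cut off from below, more so for the tracer that misses more lesions. The two tracers may therefore look more alike than they are.
- A lesion-level correlation with uptake loses the low end of the range and is weakened.
- Discordant lesions, which are central to Aim 2, have uptake on one tracer only.

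The stated goal of the study is preliminary data for estimating effect size, so a selected uptake estimate would carry forward into the next trial's planning.

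**Working it through.** **1. The plan's own figures that use uptake.** Section 10 gives 84 and 46 patients to detect r = 0.3 and r = 0.4 between a ctDNA parameter and a PET uptake parameter (80% power, Type I error 0.05). With the two-sided Fisher z formula, N = ((1.960 + 0.842) / atanh(r))² + 3:

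- r = 0.3: 84.93, which rounds up to 85 (stated 84)
- r = 0.4: 46.73, which rounds up to 47 (stated 46)

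These agree to within one patient and are not in dispute. The plan states no expected uptake value, so everything below is illustration.

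**2. Two-group illustration.** Assume avid metastases have mean SUV 5, non-avid ones sit at background b = 1 to 2, and only avid ones are recorded. The true mean is 5p + b(1 − p), where p is the avid share. The recorded mean is 5.

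| p | Where p comes from | True mean (b = 1 to 2) | Overstatement |
|---|---|---|---|
| 0.84 | Section 2.2: share of lesions seen on PSMA PET in a breast cancer series with only 2 ILC patients | 4.36 to 4.52 | 15% to 11% |
| 0.80 | Assumed | 4.20 to 4.40 | 19% to 14% |
| 0.42 | Section 2.2: "64.6% of patients with IDC had PSMA staining, versus 42.2% of those with ILC" | 2.68 to 3.26 | 87% to 53% |

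The last row is an outer bound only, because tissue staining is not PET avidity.

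**3. Continuous illustration.** Assume log-normal SUV with median M and coefficient of variation CV, recorded only above a cut of 2.5 (assumed). With s = √ln(1 + CV²) and k = ln(2.5/M)/s, the ratio of recorded to true mean is Φ(s − k)/Φ(−k).

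| M | CV | Share below cut | Recorded / true mean |
|---|---|---|---|
| 6 | 0.4 | 1% | 1.01 |
| 4 | 0.4 | 11% | 1.06 |
| 3 | 0.4 | 32% | 1.18 |
| 4 | 0.8 | 25% | 1.22 |
| 3 | 0.8 | 40% | 1.38 |

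The bias comes from low-uptake lesions. The fluciclovine ILC node figure in section 2.2 (SUVmax 6.2 ± 0.8, 3 nodes) would imply almost none.

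**4. How much depends on the call following SUV.** With normal SUV and a sharp threshold, losing 10% to 50% of lesions shifts the mean up by 0.20 to 0.80 SD. If the call correlates only 0.5 with SUV, the shift is 0.10 to 0.40 SD. If it is unrelated to SUV, the shift is zero.

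**5. Lesion-level correlation.** Under the sharp threshold, the SD of recorded values falls to u = 0.84 to 0.60 of its true value. A true r = 0.3 is then observed as r·u/√(1 − r² + r²u²), which is 0.26 to 0.19. By the formula in step 1, detecting this takes 118 to 224 observations instead of 85.

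**6. Metastasis against primary.** Take equal true uptake, 15 lesions drawn per group, the cut of 2.5 and a nominal 5% rank test.

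- If only metastases below the cut are lost, rejection is about 18% to 34% in three scenarios (M = 3 with either CV; M = 4 with CV 0.8), about 7% at M = 4 with CV 0.4, and about 5% at M = 6.
- If primaries below the cut are lost too, rejection is about 4% to 5% throughout.

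**7. What does not move.** A proven lesion negative on a tracer still counts as not detected, so detection rates, McNemar tests and concordance stand. For summed MTV and TLA, an omitted lesion contributes the same as a zero.

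**The case against.** The strongest reply has five parts.

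- **The text does not say that suspicion must come from the blinded read.** Patients may enter with suspected or proven metastases, an unblinded reconciliation follows, and the analysis sentence already covers all proven lesions. This stands in part. The link to the blinded read is inferred from order and blinding, and the plan nowhere says that such lesions go without a value. What remains is a gap between the measured and analysed sets that no instruction closes.
- **The primary may be no different.** A reader might infer that the measurement rule alone could reproduce the higher uptake in ILC nodes than in primaries reported in section 2.2. The documents do not support this. The same blinding could hide a non-avid primary, and step 6 shows that the false difference then disappears. Section 10 plans no such test, and no paired fluciclovine/PSMA uptake test either.
- **Burden is not overstated.** A reader might extend the upward bias to the summed indices in section 9. That does not follow: summed MTV and TLA are unchanged by adding a zero, and summed SUV would be too low if anything.
- **Direction is not certain for every lesion.** A metastasis missed within physiologic activity, such as in liver, need not have a low SUV. This stands, and the fix allows for it.
- **Size is assumed.** This stands. The 42.2% must not be read as the share of metastases that are PSMA-avid on PET.

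**Conclusion.** The point holds as a gap in the measurement rule with a predictable consequence. Followed in the order written, the plan gives no uptake value on a tracer for a proven metastasis not called on that tracer, while the planned analysis covers all proven lesions. Per-lesion SUV summaries in proven metastases would tend to be too high, lesion-level correlations would tend to be weakened, and discordant lesions would lack paired uptake.

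The size cannot be derived from the documents. It is about 1% if uptake is uniformly high and 11% to 15% at 84% avid under the assumed SUVs. It is larger if many lesions are negative, and nil if the call is unrelated to SUV. All of this assumes that tracer-negative lesions are left out of the analysis.

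The primary endpoint is untouched. This is a worthwhile, cheap improvement to secondary and exploratory uptake analyses in a 20-patient study; it does not invalidate the design.

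**What to change.** Keep the blinded measurements as they are. Add to sections 4.1 and 9:

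- After the unblinded reconciliation, and once reference status is known, SUVmax, SUVmean and SUVpeak are measured on both PET scans for every proven primary, locoregional and distant lesion. Where no focus was called on a tracer, the region is copied from the positive tracer or from the CT/MR correlate.
- MTV and TLA are set to zero, not missing, where nothing can be segmented on that tracer.
- Lesions lying within physiologic uptake are flagged as not evaluable for SUV on that tracer, and their number is reported.
- The uptake correlations in sections 4.1 and 9 and the index-lesion values used for ctDNA are based on this set. Any other uptake summary is labelled as covering tracer-positive lesions only.

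The cost is a few sentences of wording and a few minutes of workstation time per proven lesion by the existing readers on scans already acquired. No further scan, biopsy, reader or patient is needed. The drawbacks are some registration error in copied regions and lower reported mean uptake.
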